9.1.1.3. British Isles Lupus Assessment Group 2004 Index

The BILAG-2004 Index is a validated global disease activity index designed on the basis of the physician's intention to treat, focusing on changes in disease manifestations (not present, improving, same, worse, or new) occurring in the last 4 weeks compared with the previous 4 weeks. The instrument assesses 97 clinical signs, symptoms, and laboratory parameters across 9 organ system domains: constitutional, mucocutaneous, neuropsychiatric, musculoskeletal,

cardiorespiratory, gastrointestinal, ophthalmic, renal, and hematology. A BILAG A disease activity score is severe disease activity requiring high-dose oral or intravenous corticosteroids, immunomodulators, or high-dose anticoagulation along with high-dose corticosteroids or immunomodulators. A BILAG B disease activity score is moderate disease activity requiring low-dose oral corticosteroids, intramuscular or intra-articular corticosteroid injections, topical corticosteroids or immunomodulators, antimalarials, or symptomatic therapy. BILAG C corresponds to stable mild disease, BILAG D is inactive disease that was active previously, and BILAG E indicates that the system was never involved.

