## **6.11. Efficacy Analyses**

### **6.11.1. General Considerations**

[Table JAIM.6.3](#) includes the description, derivation and definition of missingness of the efficacy and health outcomes measures and endpoints. [Table JAIM.6.4](#) includes the description of the

analysis method, population and primary time point(s) of analysis for efficacy and health outcomes measures. Assessments collected at multiple visits will be analyzed at each visit, in addition to the primary time point. Details of each analysis will follow the general principles described under Analysis Methods in Section [6.4](#).

Table JAIM.6.3. Description and Derivation of Efficacy/Health Outcomes Measures and Endpoints

Measure	Description	Variable	Derivation/Comment	Definition of Missing
SRI-4	SRI-4 is a composite index to measure overall improvement in disease activity (SLEDAI-2K) while ensuring there is no worsening in other organ systems (BILAG and PGA)	SLE Responder Index 4	A decrease in SLEDAI-2K $\geq 4$ (from baseline), and No new BILAG A and no more than 1 new BILAB B organ domain (both compared with baseline), and No worsening in PGA (defined as an increase of 0.3 points [10 mm] from baseline).	Missing, if any component (SLEDAI, BILAG, or PGA) remains missing after each instrument-level imputation rule is applied
SLEDAI-2K	The SLEDAI-2K is a global disease activity instrument that focuses on high-impact disease manifestations across 9 organ domains: constitutional, mucocutaneous, musculoskeletal, vascular, cardiorespiratory, central nervous system, immunologic, renal, and hematologic.	SLEDAI-2K Total Score	Calculated by summing the weighted organ manifestations. For the Renal domain, when the urinary casts, hematuria, and pyuria items are “not done” or “not accessed”, they will be coded as “not present”.	If any item scores or all items are missing (not done or not assessed), but the visit occurred, data for that item can be carried forward if obtained within the previous 36 days of visit.
		Individual Organ Domain Improvement defined by SLEDAI-2K	Among patients with SLEDAI-2K score $>0$ within the organ domain at baseline and able to decrease SLEDAI-2K (from baseline) within each organ domain score, separately.	Missing if any SLEDAI-2K item for that organ domain remains missing after instrument-level imputation rules are applied.

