		Individual Organ Domain Worsening defined by SLEDAI-2K	Among patients with at least 1 SLEDAI-2K item = 0 in the organ domain score at baseline and able to increase SLEDAI-2K (from baseline) within each organ domain score, separately.	Missing if any SLEDAI-2K item for that organ domain remains missing after instrument-level imputation rules are applied.
		No worsening from baseline in SLEDAI-2K	No increment from baseline of $>0$ points in SLEDAI-2K.	Missing if any SLEDAI-2K item for that organ domain remains missing after instrument-level imputation rules are applied.
BILAG-2004	BILAG-2004 assesses 97 clinical signs, symptoms and laboratory	BILAG	A, B, C, D, or E score will be used in analyses for each of the 9 individual	Within each organ domain (except renal and hematological), any

Measure	Description	Variable	Derivation/Comment	Definition of Missing
	parameters across nine organ system domains: constitutional, mucocutaneous, neuropsychiatric, musculoskeletal, cardiorespiratory, gastrointestinal, ophthalmic, renal and hematological		organ systems.	
missing data will be assumed to be 'Not present' if there is at least 1 nonmissing item in that organ. If all items in 1 organ domain are completely missing but the visit occurred, then the letter score of that organ from the previous visit will be pulled forward, provided data can be obtained within 36 days of visit; otherwise missing except when the letter score from the last nonmissing visit is E, then E score will be pulled forward.
 
For Renal and Hematological domain, if any item is missing but there is at least 1 nonmissing item in the organ, the missing data will be assumed to be "No". If any vital/lab item with "Yes" but vital and lab value is missing, then vital/lab values can be pulled forward, provided data can be obtained within 36 days of visit; otherwise missing. After the value imputation, if the A/B/C score for the organ domain still cannot be derived, then the letter score of that organ from the previous visit will be pulled forward, provided data can be obtained within 36 days of visit; otherwise missing except when the letter score from the last nonmissing visit is E, then E score will be pulled forward.

		BILAG	Reduction of all baseline BILAG A to	Missing if any of 9 domains at

Measure	Description	Variable	Derivation/Comment	Definition of Missing

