		improvement	B/C/D and baseline BILAG B to C/D and no BILAG worsening in other organ systems, where worsening is defined as $\geq 1$ new BILAG A or $\geq 2$ new BILAG B	baseline or at the visit remain missing after instrument-level imputation rules are applied, except when the missing is at the baseline (any one or all domains) and the value at the visit is not A or B, then the other nonmissing organ domains will be used to determine the response status.
		No BILAG worsening	No new BILAG A and no $>1$ new BILAG B disease activity score (both compared with baseline), where worsening is defined as $\geq 1$ new BILAG A or $\geq 2$ new BILAG B, both compared with the baseline. The baseline BILAG A improved to BILAG B at the visit will not be considered as the new BILAG B.	Missing if any of 9 domains at baseline or at the visit remains missing after instrument-level imputation rules are applied except when the baseline (any one or all domains) is BILAG A and the value at the visit is missing, then the other nonmissing organ domains will be used to determine the response status.
		Individual Organ Domain Improvement Defined by BILAG	Among patients with BILAG A or B at baseline and able to reduce the baseline BILAG A to B/C/D and BILAG B to C/D for each organ domain, separately.	Missing if baseline or value remains missing after instrument-level imputation rules are applied.
		Individual Organ Domain Worsening Defined by BILAG	Among patients without BILAG A at baseline, an increment of baseline BILAG B/C/D/E to A or baseline BILAG C/D/E to B for each organ domain, separately.	Missing if baseline or value remains missing after instrument-level imputation rules are applied.
Physician's Global Assessment of Disease Activity	The PGA is the physician's assessment of the patient's overall disease activity due to SLE. It is scored using a visual analog scale	PGA score PGA category	Permitted range of values is from 0 to 100 mm. PGA categories are defined as: None (0) = '0 mm', Mild ( $>0$ and $<1.5$ ) = ' $>0$ to $<50$ mm', Moderate ( $\geq 1.5$ to $\leq 2.5$ )	If the visit occurred, data can be carried forward if obtained within 36 days of visit; otherwise missing.

Measure	Description	Variable	Derivation/Comment	Definition of Missing

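### In the renal and hematological BILAG domains, an item marked Yes with no usable value can be scored E (never involved), which can hide a new A or B in SRI, BICLA and BILAG organ worsening

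*SAP*

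**What the plan says.** The rule is in SAP Section 6.11.1, Table JAIM.6.3, BILAG-2004 row, last column. For the renal and hematological domains it runs in this order:

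1. A missing item becomes *No* if at least one other item in the domain is present.
2. For an item marked *Yes* the text continues: "but vital and lab value is missing, then vital/lab values can be pulled forward, provided data can be obtained within 36 days of visit". If there is no such value, it stays missing.
3. "After the value imputation, if the A/B/C score for the organ domain still cannot be derived", the letter from the previous visit is used, "provided data can be obtained within 36 days of visit". Failing that, the domain is "otherwise missing except when the letter score from the last nonmissing visit is E, then E score will be pulled forward".

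The last exception has no time limit, and no step excludes a domain that holds a *Yes*.

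Protocol Section 9.1.1.3 gives the meaning of the letter: "BILAG E indicates that the system was never involved". In the same SAP table, the no-worsening component fails with one or more new A, or two or more new B, compared with baseline. BILAG organ worsening counts "an increment of baseline BILAG B/C/D/E to A or baseline BILAG C/D/E to B for each organ domain, separately". SRI and BICLA both use BILAG after these rules have been applied. For SLEDAI-2K the table says that "data for that item can be carried forward if obtained within the previous 36 days of visit", and PGA has a 36-day limit too. Neither has an exception like the one for E.

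**The concern.** Step 1 already settles ordinary missing items in a partly completed domain. Such a domain therefore reaches the letter-level carry-forward chiefly through a *Yes* without a value. In that case the visit's own record points towards involvement, and the rule assigns the one letter that denies any involvement, past or present.

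Protocol Section 9.1.1.1 says that the BILAG part of SRI is there to ensure that improvement does not come with worsening in other organ systems. A previously uninvolved organ becoming active is what that part has to detect, and it is the case that the rule can hide. BILAG organ worsening is affected directly, because a move from E to A or B is one of its defining events.

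**Working it through.** The plan gives no figure to reproduce. The check traces the rule, compares its time limit with the visit schedule, tests its direction, and then sizes it under stated assumptions.

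**1. Does the 36-day window help at scheduled visits?** Inputs are the study days and windows in Protocol Table JAIM.1. Minimum gap = (later day − its window) − (earlier day + its window).

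- Week 0 to 4: (29 − 4) − 1 = 24 days (maximum 32), so within 36.
- Week 4 to 12: (85 − 7) − (29 + 4) = 45.
- Week 12 to 24: (169 − 10) − (85 + 7) = 67.
- Week 24 to 36, 36 to 48 and 48 to 60: 84 − 10 − 10 = 64 each.
- Week 60 to 84: (589 − 14) − (421 + 10) = 144.
- Week 84 to 108, 108 to 132 and 132 to 156: 168 − 14 − 14 = 140 each.

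From Week 12 on, unscheduled data aside, no earlier scheduled value or letter is recent enough. Step 3 then ends either in a missing domain or in a carried E. At Week 156, the key time point, an E carried from a scheduled visit is at least 140 days old.

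**2. Direction.** Take a domain that was E at baseline and at the last nonmissing visit. The table shows whether the patient passes the no-worsening component.

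| True letter now | New B in other domains | Under true letter | Under carried E |
|---|---|---|---|
| A | 0 or 1 | fail | pass |
| B | 0 | pass | pass |
| B | 1 | fail | pass |
| C or E | 0 or 1 | pass | pass |

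Every change goes from fail to pass. It needs a hidden new A or a hidden second new B. For BILAG organ worsening, any hidden A or B is a lost event.

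**3. Size for a response rate.** None of the three inputs is in the documents, so all are assumed:

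- f, share of patients reached by the rule: 0.5% to 5%
- q, share of these whose true letter fails the component: 10% to 50%
- r, share meeting all other components: 40% to 65%

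Overstatement = f × q × r.

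- Low: 0.005 × 0.10 × 0.40 = 0.02 percentage points.
- High: 0.05 × 0.50 × 0.65 = 1.6 percentage points.

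If every affected would-be responder is instead counted as a non-responder, the rate falls by f × r: 0.005 × 0.40 = 0.2 points to 0.05 × 0.65 = 3.25 points. A share 1 − q of that fall is patients who would truly have passed.

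**4. What does leaving the domain missing change in the observed analysis?** Assume a true SRI-4 rate of 50%, 1% of patients with a hidden new A, and 55% of those meeting the other components.

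- Carried E: 50 + 0.55 = 50.55%.
- Domain missing: 50 / 99 = 50.51%.
- Counted as failing: 50 / 100 = 50%.

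For organ worsening, assume a true rate of 3.0% with 5%, 10% or 20% of events hidden.

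- Carried E: 3.0 × (1 − 0.05, 0.10, 0.20) = 2.85%, 2.70%, 2.40%.
- Domain missing: 2.85 / 99.85 = 2.85%, 2.70 / 99.70 = 2.71%, 2.40 / 99.40 = 2.41%.

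In the observed analysis most of the loss comes from the absent value, not from the carried E.

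**The case against.** Several objections have force.

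- *The meaning of Yes.* The SAP does not define it. That it means the feature is present is inferred from *No* standing where the other domains use a not-present default. This stands, and it is why the point speaks of possible involvement. A reader might infer that the investigator has declared the organ affected; the documents do not go that far.
- *Other components.* SLEDAI-2K scores proteinuria, thrombocytopenia and leukopenia separately (Protocol Section 9.1.1.2), with a 36-day limit. If the same laboratory value is missing there, SRI or BICLA may itself be missing and not a response. PGA must not worsen either. This stands in part: urinary casts, hematuria and pyuria that were not done are coded as not present, and SRI needs only a net SLEDAI-2K fall.
- *Age of the E.* A reader might infer that E is routinely carried for up to 1,092 days (Day 1 to Day 1093). That would need no derivable letter at any visit between Week 0 and Week 156, although BILAG and the related laboratory tests are scheduled at every visit. It is a theoretical extreme.
- *A 36-day limit on E everywhere.* A reader might infer that E should have the same limit as A to D in all domains. Outside the renal and hematological domains, E is carried only when every item is missing, so no entry contradicts it. Never-involved status is plausibly stable. One missing domain generally makes the no-worsening component missing, so a limit could discard otherwise complete SRI and BICLA results from Week 12 on. The documents do not support that change.
- *Worst-case coding.* NRI in SAP Section 6.4.2.2 does not name an on-treatment patient with one unscorable domain. Counting such patients as failures will misclassify some true C and single-B cases. This stands as a cost of the fix.

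**Conclusion.** The rule is wrong as written for one case: a renal or hematological domain with an item marked *Yes*, no value within 36 days, no derivable letter, and a last nonmissing letter of E. The assigned score contradicts the visit's own record, and its error goes in one direction only. It can overstate SRI-4 to SRI-8, BICLA and the no-worsening proportion, and it understates BILAG organ worsening.

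The size is unknown and probably small. The range of 0.02 to 1.6 points rests entirely on assumed inputs and takes no account of patients whose composite is missing for other reasons.

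A reader might infer a material bias that the fix would remove. The observed-analysis figures do not support this: 50.55% against 50.51%, and 2.85% either way at a 5% hidden share. Only the NRI analysis moves noticeably. Nor is a false-positive test at issue. Efficacy is not primary (SAP Section 6.11.2), no between-group inference is planned (SAP Section 6.1), and BICLA and the BILAG organ analyses are additions in the SAP. The case for changing the text is that the score is contradictory and the repair costs almost nothing.

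**What to change.** - Add one sentence to the renal and hematological part of the BILAG-2004 cell: the E exception does not apply when any item in that domain is *Yes* at the visit.
- State the consequence. The domain is missing in the observed analysis, and in the NRI analysis the patient counts as not meeting the BILAG component. SAP Section 6.4.2.2 needs a matching line, because it does not name this case.
- Report how many SRI, BICLA and organ-worsening results rest on a carried E or on a domain left missing by this sentence.
- In the other domains leave the E rule as it is. Reporting the number of carried E scores is enough there.

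The cost is a sentence or two of SAP text, a small change to the derivation and a count in the output. The downside is a few more missing or non-response results, some of which may truly be a C or a single tolerated B. The reported counts show how far this matters.

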(PGA)	where 0 mm indicates no disease activity and 100 mm indicates the most severe disease activity possible. There are benchmarks of 0 (0 mm), 1 (33 mm), 2 (67 mm), and 3 (100 mm) on the line corresponding to no, mild, moderate, and severe SLE disease activity, respectively.		= '≥50 mm to ≤83mm', Severe (>2.5) = '>83mm'.	
		No worsening in PGA	Worsening is defined as an increase of ≥0.3 points (10 mm) from baseline. Therefore, no worsening is defined as any decrease, no change, or <0.3 points (10 mm) increase from baseline.	Missing if baseline or value remains missing after instrument-level imputation rules are applied.
		PGA ≤1	PGA ≤33 mm	Missing if value remains missing at the visit after instrument-level imputation rules are applied.
BICLA	BICLA is a composite index to measure overall improvement in disease activity (BILAG) while ensuring there is no worsening in other organ systems (SLEDAI-2K and PGA)	BICLA	
 
Reduction of all baseline BILAG A to B/C/D and baseline BILAG B to C/D and no BILAG worsening in other organ systems, where worsening is defined as ≥1 new BILAG A or ≥2 new BILAG B
 
No worsening from baseline in SLEDAI-2K, where worsening is defined as an increase from baseline of >0 points in SLEDAI-2K
 
No worsening from baseline in participants' lupus disease activity, where worsening is defined by an increase ≥0.30 points on a 3-point PGA visual analogue scale (VAS).
 
	Missing if any component (BILAG, SLEDAI or PGA) remains missing after each instrument level imputation rule is applied.
Cutaneous Lupus Erythematosus Disease Area and Severity Index (CLASI)	The CLASI is a validated instrument to assess cutaneous manifestations of SLE consisting of 2 scores: 
 
Activity
 
Damage
 
	Total Activity Score	Calculated within tablet system with edit checks; no additional derivation.	Within tablet system: if any item scores, but not all, are missing then impute a score of 0 for the missing item(s). For completely missing questionnaires, data can be carried forward if obtained within 36 days of visit; otherwise missing.

Measure	Description	Variable	Derivation/Comment	Definition of Missing

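### SAP Table JAIM.6.3: the 'No BILAG worsening' row lacks the missing-baseline exception given to BILAG improvement, so observed SRI can be missing when recorded data settle the status

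*SAP*

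**What the plan says.** Everything here is in SAP Section 6.11.1, Table JAIM.6.3, unless another place is named.

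- **'No BILAG worsening'.** The default is "Missing if any of 9 domains at baseline or at the visit remains missing after instrument-level imputation rules are applied". The only relief is "except when the baseline (any one or all domains) is BILAG A and the value at the visit is missing", in which case the other domains decide. The row also states: "The baseline BILAG A improved to BILAG B at the visit will not be considered as the new BILAG B".
- **'BILAG improvement'.** The default is the same, but the relief is "except when the missing is at the baseline (any one or all domains) and the value at the visit is not A or B". Its definition includes the same worsening test (at least one new A, or at least two new Bs).
- **SRI-4.** Its BILAG part is the no-worsening criterion. The composite is "Missing, if any component (SLEDAI, BILAG, or PGA) remains missing after each instrument-level imputation rule is applied". Protocol Section 9.1.1.5 builds SRI-5 to SRI-8 in the same way, with a larger SLEDAI-2K reduction.
- **BICLA.** Its BILAG part carries the improvement row's wording: "Reduction of all baseline BILAG A to B/C/D and baseline BILAG B to C/D and no BILAG worsening in other organ systems". It has the matching composite rule, "Missing if any component (BILAG, SLEDAI or PGA) remains missing after each instrument level imputation rule is applied".
- **Instrument-level imputation, applied first.** In most domains "missing data will be assumed to be 'Not present' if there is at least 1 nonmissing item in that organ"; renal and hematological items are set to 'No' in the same situation. For a wholly missing domain, the previous letter is pulled forward within 36 days, and an E without that limit.
- **Baseline** (SAP Section 6.3) is the last nonmissing value before the relevant first dose.
- **Analyses** (SAP Table JAIM.6.4). SRI-4 and the stand-alone BILAG no-worsening endpoint are each summarised as observed and with NRI. SRI-4 is restricted to mITT patients with baseline SLEDAI-2K of at least 4.

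**The concern.** Two neighbouring rows apply one worsening test but disagree on when it can be evaluated. For a domain missing at baseline and C, D or E at the visit, the improvement row treats the absence of worsening as known. The no-worsening row treats it as unknown. No reason is given. The baseline-A exception shows that the no-worsening row already accepts the principle of scoring a patient when the incomplete domain cannot have worsened; it applies that principle to only one of the situations where it holds.

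Baseline does not change over follow-up, so an unresolved baseline domain carries through to every visit. It affects SRI-4 (the first-listed secondary efficacy endpoint), SRI-5 to SRI-8, and the stand-alone BILAG endpoint. The loss is not all in one direction: a patient with a recorded new A in another domain, who is certainly a non-responder, also becomes missing.

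**Working it through.** The plan gives no figure to reproduce, so the check is logical first and arithmetical second.

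**Step 1: domain level.** Baseline and visit values each lie in {A, B, C, D, E, missing}. Of the 6 × 6 = 36 pairs, 25 are complete and 11 have at least one value missing. A new A needs visit A with baseline not A. A new B needs visit B with baseline C, D or E, because the plan excludes A-to-B.

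| Baseline → visit | Possible contribution | Certain not to have worsened? | Covered by no-worsening row? | Covered by improvement row? |
|---|---|---|---|---|
| A → missing | none | yes | yes | no |
| B → missing | none or new A | no | no | no |
| C, D or E → missing (3 pairs) | none, new A or new B | no | no | no |
| missing → A | none or new A | no | no | no |
| missing → B | none or new B | no | no | no |
| missing → C, D or E (3 pairs) | none | yes | **no** | yes |
| missing → missing | none, new A or new B | no | no | no |

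Absence of worsening is certain in 4 pairs, and the no-worsening row covers 1 of them. The improvement criterion is certain to be met in 3 pairs (missing to C, D or E), and its row covers all 3. The difference for A-to-missing is proper: baseline A cannot worsen, but improvement cannot be judged without the visit value.

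**Step 2: patient level, one domain missing at baseline.**

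- Visit value C, D or E: the other eight domains decide.
- Other domains already show at least one new A or two new Bs: worsening is certain, whatever the incomplete domain holds.
- Visit value B: it adds 0 or 1 new B, so the status is open only if the other domains hold exactly one new B and no new A.
- Visit value A: open unless the other domains already prove worsening.

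The no-worsening row returns missing in all four situations, and SRI-4 follows it through the component rule.

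**Step 3: how many patients.** The documents give no missingness rate. Let q be the share of patients in whom a given domain is still missing at baseline after imputation (assumed), with N = 1100, the planned enrolment in Protocol Section 5.2.

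- Domains missing together (whole form absent): share = q.
- Domains missing independently: share = 1 − (1 − q)^9.

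| q (assumed) | Together | Independent |
|---|---|---|
| 0.2% | 0.2%, about 2 | 1.8%, about 20 |
| 0.5% | 0.5%, about 6 | 4.4%, about 49 |
| 1% | 1%, 11 | 8.6%, about 95 |

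These counts are too high for SRI, which uses only mITT patients above a SLEDAI-2K threshold. SAP Section 6.2 also removes the China extended-enrolment patients and one site.

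**Step 4: possible effect under NRI.** If such patients were all counted as non-responders, the response rate would fall by (true rate) × (share). With the Phase 2 Week 24 SRI-4 rates in Protocol Section 3.1 (47.6% to 64.4%) as illustration, each 1% of patients so counted lowers the rate by 0.476 × 1 = 0.48 to 0.644 × 1 = 0.64 percentage points.

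**The case against.** The strongest reply has four parts.

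**The case is rare.** A domain counts as missing at baseline only after item-level filling, the 36-day and E pull-forward, and the last-nonmissing baseline rule. The scales are physician-completed on an electronic device (Protocol Section 2). This stands, and it is why the lower end of the range is the more plausible one.

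**The present rule is neutral to outcome.** It drops an unresolved baseline whatever the visit shows. Adding only the missing-to-C/D/E exception would admit favourable visits and leave A or B visits missing. This also stands, and it means that copying the improvement row's sentence alone is not enough. The sponsor already accepts this dependence for BILAG improvement, so it does not justify the difference between the rows.

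**SRI-4 and BICLA differ by design.** A reader might infer that the two composites rest on different patients only because of this rule. The documents do not support that: SRI-4 is limited to baseline SLEDAI-2K of at least 4 while BICLA uses the full mITT population, and BICLA properly uses a different BILAG variable.

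**NRI still classifies some of these patients.** A reader might also infer that an affected patient can never be scored for SRI-4. Under SAP Section 6.4.2.2, discontinuation or prohibited medication makes the patient a non-responder for that interval regardless of component missingness. The statement therefore holds only for the observed analysis. What remains open is an on-treatment patient whose SRI cannot be derived, a case that section does not address.

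**Conclusion.** The inconsistency is real and follows from the text. In the observed analysis, a baseline domain still missing after all imputation makes SRI-4 to SRI-8 and the stand-alone no-worsening endpoint missing at every visit, including visits where recorded data settle the status. Under NRI, the handling of such a patient on treatment is unstated.

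The size is unknown and probably small: about 2 to 11 of 1100 if domains go missing together, or 20 to 95 if independently, at an assumed 0.2% to 1% per domain, and fewer in the SRI subset. The upper figures should not be read as an estimate, since they depend on independence that nothing in the documents supports.

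The stakes are limited. Safety is primary, SRI-4 is a descriptive secondary endpoint, and SAP Section 6.1 plans no between-group inference unless otherwise stated. The point merits correction because the correction is cheap and relies on recorded data, not because a conclusion is shown to change.

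**What to change.** In the 'No BILAG worsening' row of SAP Table JAIM.6.3:

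1. Keep the baseline-A exception.
2. Add that a domain missing at baseline with a recorded visit value other than A or B is treated as not worsened, and that status is then determined from the other domains.
3. Add that worsening is scored as present when the nonmissing domains already show at least one new A or at least two new Bs, even if another domain is missing. This keeps the change from admitting only favourable visits.

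In SAP Section 6.4.2.2, state that a status still undetermined after these rules counts as non-response in the NRI analysis.

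The sponsor could also settle a missing-to-B domain when no other domain holds a new A or new B, since one new B is allowed. That would shrink the undetermined remainder further.

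The cost is a few sentences and the matching derivation code, with no new data. One downside remains: in the observed analysis, evaluability still depends slightly on the visit value for the few cases left undetermined. Reporting their number by visit would show whether that matters.
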